4.3.3 Prophylactic Treatment

The following premedications must be administered prior to each infusion of ocrelizumab to reduce the frequency and severity of IRRs:

- 100 mg intravenous methylprednisolone (or an equivalent), administered by slow IV infusion, to be completed approximately 30 minutes and not less than 25 minutes prior to each ocrelizumab infusion
- Antihistamine, via oral, intramuscular or IV route to be completed approximately 30-60 minutes and not less than 25 minutes prior to each ocrelizumab infusion (the antihistamine should be the first premedication to be administered)
- The addition of an antipyretic (e.g., acetaminophen/paracetamol) may also be considered

Any overdose or incorrect administration of methylprednisolone and antihistaminic drug should be noted on the Pre-Infusion Prophylactic Treatment eCRF. Adverse events associated with an overdose or incorrect administration of methylprednisolone and antihistaminic drug should be recorded on the Adverse Event eCRF.

Patients administered a sedating antihistamine for the treatment or prevention of IRRs should be given appropriate warnings concerning drowsiness and potential impairment of ability to drive or operate machinery.

4.3.4 Investigational Medicinal Product Handling and Accountability

The IMP required for completion of the main study (ocrelizumab) will be provided by the Sponsor where required by local health authority regulations. The study site (i.e., investigator or other authorized personnel [e.g., pharmacist]) is responsible for

maintaining records of IMP delivery to the site, IMP inventory at the site, IMP use by each patient, and disposition or return of unused IMP, thus enabling reconciliation of all IMP received, and for ensuring that patients are provided with doses specified by the protocol.

The study site should follow all instructions included with each shipment of IMP. The study site will acknowledge receipt of IMP supplied by the Sponsor, using the interactive voice/Web response system (IxRS) to confirm the shipment condition and content. Any damaged shipments will be replaced. The investigator or designee must confirm that appropriate temperature conditions have been maintained during transit, *either by time monitoring (shipment arrival date and time) or temperature monitoring,* for IMP received and that any discrepancies have been reported and resolved before use of the IMP. All IMP must be stored in a secure, environmentally-controlled and monitored (manual or automated) area in accordance with the labeled storage conditions, with access limited to the investigator and authorized staff.

Only patients enrolled in the study may receive IMP, and only authorized staff may supply or administer IMP.

The IMP will either be disposed of at the study site according to the study site's institutional standard operating procedure or returned to the Sponsor with the appropriate documentation. The site's method of destroying Sponsor-supplied IMP must be agreed to by the Sponsor. The site must obtain written authorization from the Sponsor before any Sponsor-supplied IMP is destroyed, and IMP destruction must be documented on the appropriate form.

Accurate records of all IMP received at, dispensed from, returned to, and disposed of by the study site should be recorded on the drug accountability log.

Refer to the Dose Preparation Guidelines and/or the ocrelizumab IB for information on IMP handling, including preparation and storage, and accountability.

4.3.5 Continued Access to Ocrelizumab

Patients may be eligible to receive ocrelizumab as part of an extension study (MN39158) to evaluate long-term effectiveness and safety, as described in Section 3.1.3.

The Sponsor will offer continued access to Roche IMP (ocrelizumab) free of charge to eligible patients in accordance with the Roche Global Policy on Continued Access to Investigational Medicinal Product, as outlined below.

A patient will be eligible to receive Roche IMP (ocrelizumab) after completing the study if all of the following conditions are met:

• The patient has a life-threatening or severe medical condition and requires continued Roche IMP treatment for his or her well-being

Ocrelizumab—F. Hoffmann-La Roche Ltd

50/Protocol MA30143, Version 10.0

- There are no appropriate alternative treatments available to the patient
- The patient and his or her doctor comply with and satisfy any legal or regulatory requirements that apply to them

A patient will not be eligible to receive Roche IMP (ocrelizumab) after completing the study if any of the following conditions are met:

- The Roche IMP is commercially marketed in the patient's country and is reasonably accessible to the patient (e.g., is covered by the patient's insurance or wouldn't otherwise create a financial hardship for the patient)
- The Sponsor has discontinued development of the IMP or data suggest that the IMP is not effective for RMS and PPMS
- The Sponsor has reasonable safety concerns regarding the IMP as treatment for RMS and PPMS
- Provision of the Roche IMP is not permitted under the laws and regulations of the patient's country

The Roche Global Policy on Continued Access to Investigational Medicinal Product is available at the following Web site:

http://www.roche.com/policy_continued_access_to_investigational_medicines.pdf

4.4 CONCOMITANT THERAPY

Concomitant therapy includes any medication (e.g., prescription drugs, over-the-counter drugs, vaccines, herbal or homeopathic remedies, nutritional supplements) used by a patient in addition to protocol-mandated treatment within 6 weeks prior to the screening visit to the study completion/ discontinuation visit. All such medications should be reported to the investigator and recorded on the Concomitant Medications eCRF.

4.4.1 Prohibited Therapy

No formal drug-drug interaction studies have been conducted with ocrelizumab, as no drug-drug interactions are expected via the Cytochromes P450, other metabolizing enzymes or transporters.

Ocrelizumab is a monotherapy and has not been studied in combination with other DMTs. As with other immunomodulatory therapies, exercise caution when initiating ocrelizumab after an immunosuppressive therapy, and when initiating another therapy after ocrelizumab, taking into consideration the potential for overlapping pharmacodynamic effects.

Immunosuppressants, lymphocyte-depleting agents, or lymphocyte-trafficking blockers should NOT be administered while patient is B-cell depleted.

Hypotension, as a symptom of IRR, may occur during ocrelizumab IV infusions. Therefore, withholding antihypertensive treatments should be considered for 12 hours prior to and throughout each ocrelizumab infusion.

Ocrelizumab—F. Hoffmann-La Roche Ltd 51/Protocol MA30143, Version *10.0*

See the Ocrelizumab IB for a more detailed safety profile. In addition, the Investigator should contact the Medical Monitor if questions arise regarding medications not listed above.

4.5 STUDY ASSESSMENTS

The schedule of activities to be performed during the main study is provided in Appendix 1. All activities must be performed and documented for each patient.

4.5.1 Informed Consent Forms and Screening Log

Written informed consent for participation in the study must be obtained before performing any study-related procedures. Informed Consent Forms for enrolled patients and for patients who are not subsequently enrolled will be maintained at the study site.

All screening evaluations must be completed and reviewed to confirm that patients meet all eligibility criteria and none of the exclusion criteria before enrolment. The investigator will maintain a screening log to record details of all patients screened and to confirm eligibility or record reasons for screening failure, as applicable.

4.5.2 Medical History, Concomitant Medication, and Demographic Data

Patients' demographics (age, gender, self-reported race, and educational level), and neurological examination will be collected. Medical History will include clinically significant diseases, surgeries, reproductive status, smoking history, and all medications (e.g., prescription drugs, over-the-counter drugs, vaccines, herbal or homeopathic remedies, and nutritional supplements) used by the patient within 6 weeks prior to the screening visit:

MS disease history: First MS symptom: date, symptoms, severity, MRI. Diagnosis of MS: Date, disease status, (EDSS, relapses, MRI) and, when available, criteria on which the diagnosis is based. Baseline disease status: EDSS, Number of relapses in the previous year, MRI lesions

4.5.3 Physical Examinations

A complete physical examination should include an evaluation of head, eye, ear, nose, and throat (HEENT), cardiovascular, dermatological, musculoskeletal, respiratory, and gastrointestinal systems. The following assessments will also be conducted: neurological examination (see Section 4.5.5), relapse description, EDSS (see Section 4.5.6), and MRI (see Section 4.5.7). Changes from baseline abnormalities should be recorded in patient notes. New or worsened clinically significant abnormalities not related to MS should be recorded as adverse events on the Adverse Event eCRF. Height and weight will be measured at screening only. See Appendix 1 (Schedule of Assessments) for the timing of these assessments.

Ocrelizumab—F. Hoffmann-La Roche Ltd 52/Protocol MA30143, Version 10.0

4.5.4 Vital Signs

Vital signs will include measurements of heart rate, systolic and diastolic blood pressures.

Vital signs should be taken within 45 minutes prior to the premedication methylprednisolone (or an equivalent) infusion. In addition, vital signs should be obtained prior to the ocrelizumab infusion, then every 15 minutes (\pm 5 minutes) for the first hour, followed by every 30 minutes (\pm 10 minutes) until 1 hour after the end of the infusion. Vital signs will be reported in the eCRF only in case of an IRR.

Vital sign measurements will be performed as outlined in the schedule of assessments (see Appendix 1). Record abnormalities observed before enrolment on the General Medical History and Baseline Conditions eCRF. At subsequent visits, record new or worsened clinically significant abnormalities on the Adverse Event eCRF (as presented in Section 5.3.5.6).

4.5.5 Neurological Examinations

Neurological examinations will be used to distinguish relapse in MS from another neurological (non-MS) disorder. Potential relapses should be recorded throughout the treatment period. See Appendix 1 (Schedule of Assessments) for the timing of these assessments.

A protocol-defined MS relapse is an occurrence of new or worsening neurological symptoms attributable to MS that meets the following criteria:

- Symptoms must persist for >24 hours and should not be attributable to confounding clinical factors (e.g., fever, infection, injury, adverse reactions to medications)
- Symptoms should be preceded by neurological stability for at least 30 days
- Symptoms should be accompanied by new objective neurological worsening determined with a timely EDSS/ Functional Systems Score (FSS) assessment, consistent with an increase of at least:
 - ≥0.5 points on EDSS scale
 - or ≥2 points on one of the following FSS scales: pyramidal, ambulation, cerebellar, brainstem, sensory, or visual
 - or ≥1 point on two or more of the following FSS scales: pyramidal, ambulation, cerebellar, brainstem, sensory, or visual

Episodic spasms, sexual dysfunction, fatigue, mood change or bladder or bowel urgency or incontinence will not suffice to establish a relapse (Please note: Sexual dysfunction and fatigue need not be scored).

All patients with new neurological symptoms suggestive of a relapse should have an EDSS/FSS assessment performed as soon as possible, ideally within 7 days of the

Ocrelizumab—F. Hoffmann-La Roche Ltd

53/Protocol MA30143, Version 10.0

onset of symptoms. EDSS/FSS data is needed to allow the sponsor to confirm whether the reported clinical relapse meets the criteria for a protocol-defined relapse.

Please note: All MS relapses (i.e., regardless of whether they may meet criteria for a protocol-defined relapse which will be adjudicated by the Sponsor based on the above criteria) will be recorded on a pre-specified eCRF "MS relapse" form. MS relapses should not be reported as an Adverse Event, unless they are serious.

As infection is a potentially serious complication of B cell-depleting therapy, investigators will also screen patients for signs and symptoms of any CNS infections and specifically PML by evaluating neurological deficits localized to the cerebral cortex, such as cortical symptoms/signs, behavioral and neuropsychological alteration, retrochiasmal visual defects, hemiparesis, cerebellar symptoms/signs (e.g., gait abnormalities, limb incoordination). Patients with suspected PML should be withheld from ocrelizumab treatment until PML is ruled out by complete clinical evaluation and appropriate diagnostic testing. A patient with confirmed PML should be withdrawn from the study. PML should be reported as a serious adverse event (with all available information) with immediate notification of the Medical Monitor. Please refer to Appendix 5 for guidance for diagnosis of PML.

Cognitive status: The cognitive status of the patient will be evaluated at baseline, and further yearly for the full duration of the trial with the use of BICAMS components.

4.5.6 Assessment of Disability

Disability in MS will be measured by the EDSS and MSFC. See Appendix 1 (Schedule of Assessments) for the timing of these assessments.

The EDSS is based on a standard neurological examination, incorporating seven functional systems (pyramidal, cerebellar, brainstem, sensory, bowel and bladder, visual, and cerebral rated and scored as FSS. Each FSS is an ordinal clinical rating scale ranging from 0 to 5 or 6. These ratings are then used in conjunction with observations and information concerning ambulation and use of assistive devices to determine the EDSS score (*i.e., ambulation score 0 to 12*). When determining the EDSS step, the Visual and the Bowel and Bladder FSS will be converted to a lower score as per the Neurostatus instructions. The original unconverted score should be recorded in the respective eCRF page. The EDSS is a disability scale that ranges in 0.5-point steps from 0 (normal) to 10 (death) (see Appendix 3).

Disability progression has been defined as an increase of ≥ 1.0 point from the baseline EDSS score that is not attributable to another etiology (e.g., fever, concurrent illness, or concomitant medication) when the baseline score is 5.5 or less, and ≥ 0.5 when the baseline score is above 5.5. For patients with an EDSS of 0, progression is defined as a change >=1.5 points Disability progression is considered confirmed when the increase in the EDSS is confirmed at a regularly scheduled visit at least 24 weeks after the initial documentation of neurological worsening.

Ocrelizumab—F. Hoffmann-La Roche Ltd 54/Protocol MA30143, Version 10.0

CDI is defined as an improvement of 1 point on the EDSS score confirmed at a regular scheduled visit at least 24 weeks after the initial documentation of neurological worsening (measured only patients with a baseline EDSS of \geq 2.0).

Stable disability is defined as a difference in EDSS score of no greater than ± 0.5 at the end of each year compared with baseline scores, worsened disability as an increase in EDSS score of > 0.5 at the end of each year compared with baseline, and improved disability as a reduction in EDSS score of > 0.5 at the end of each year compared with baseline.

MSFC is a score combining a measure of lower limb function (T25FWT), upper limb function (9HPT) and cognitive function (PASAT) used to detect disability progression in MS trials.

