2. OBJECTIVES AND ENDPOINTS

The main study will evaluate the effectiveness and safety of ocrelizumab in patients who are in early stage of RRMS.

Specific objectives and corresponding endpoints for the study are outlined below.

Objectives	Corresponding Endpoints
Primary Objective:	
 To evaluate the effectiveness of ocrelizumab in early stage of RRMS 	 Evaluate clinical measures related to disease progression over 4 years in patients in the early stage of their RRMS disease
Overview of the effectiveness measures:	
 Different effectiveness measures 	Related to disability progression:
evaluated for ocrelizumab in early stage of RRMS	 Time to onset of CDP sustained for at least 24 weeks and 48 weeks

Table 1 Objectives and Corresponding Endpoints

Objectives	Corresponding Endpoints
	 Proportion of patients who have confirmed disability improvement (CDI), CDP for at least 24 weeks and 48 weeks at year 1, 2 and 4
	 Proportion of patients who have improved, stable or worsened disability compared with baseline measured by EDSS annually
	 Mean change from baseline in EDSS score over the course of the study
	Other clinical measures and composite endpoints:
	 Time to first protocol-defined event of disease activity
	Time to first relapse
	 Annualized relapse rate
	 Proportion of patient relapse free by week 48, 96, 144 and 192
	 Proportion of patients with no evidence of protocol- defined disease activity (NEDA) over week 96, week 144 and week 192 where disease activity is defined as at least one the following events: protocol-defined relapse; CDP based on increases in EDSS; a T1 Gd- enhanced lesion after Week 8; or a new and/or enlarging T2 hyperintense lesion on MRI after Week 8 compared to the Week 8 MRI scan.
	 Proportion of patients with no evidence of progression (NEP) defined as no progression sustained for at least 24 weeks on all of the following three components (CDP; 20% increase in timed 25 Foot Walk Test [T25FWT]; 20% increase in timed 9 hole peg test [9HPT]) between baseline and week 96/192
	 Proportion of patients with no evidence of progression sustained for at least 24 weeks and no active disease (NEPAD) defined as no progression on all of the three components of NEP (CDP, T25FWT, 9HPT), no new relapse and no enlarging or new T2 or T1 Gd- enhancing lesion between baseline and week 96/192

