Based on the results of the primary analysis of the shorter infusion substudy, patients will be allowed to switch from the conventional ocrelizumab infusion (~3.5 hours) to the shorter ocrelizumab infusion (~2.0 hours) at any visit after the Week 24 visit based on the schedules of infusion as per the protocol, after providing written informed consent and in agreement with their treating physician, provided they have not experienced any previous serious IRRs with ocrelizumab treatment. While on the shorter infusion, the patients can switch back to the conventional infusion, in agreement with their treating physician. If patients develop a serious IRR while on the shorter infusion, they will be switched to the conventional infusion and should not be restarted on the shorter infusion at any following infusion visit.

*All l*aboratory samples can be taken up to 2 weeks prior to the scheduled study visit. Local laboratory results for hematology, biochemistry and CD4 should be available prior to dosing as they are re-treatment criteria. Local laboratory results for CD8 and CD19 may be available later, as they do not need to be verified prior to re-treatment. Samples for NfL, anti-drug antibodies (ADA), and ocrelizumab concentration are collected and sent to the central laboratory for analysis. Please see Section 4.5.8 for further details

After the end of treatment period visit of the last enrolled patient, approximately 24 weeks and 48 weeks may be needed to allow the confirmation of the last event of the 24-week and 48-week CDP (CDP/CDI confirmation visit). For those patients presenting with an EDSS change at the end of the treatment period and who roll over to the LTE study (Study MN39158), the 24-week and 48-week CDP confirmation visits will occur during the LTE study (Study MN39158). For patients who discontinue the study (e.g., move onto commercial ocrelizumab, or start treatment with another DMT), the EDSS CDP confirmatory assessments will not be performed.

Sub-studies will be conducted in selected countries according to local approvals and procedures. Please refer to Appendices 8, 9, and 10 for the sub-study protocols.

Criteria for Re-Treatment with Ocrelizumab

Prior to re-treatment with ocrelizumab, patients will be evaluated for the following conditions and laboratory abnormalities. If any of these are present prior to re-dosing, further administration of ocrelizumab should be suspended until these are resolved or withheld indefinitely:

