6. STATISTICAL CONSIDERATIONS AND ANALYSIS PLAN

The analysis of this open label, single arm study will be descriptive and primarily based on descriptive statistical methods. Unless otherwise specified, statistical tests will be exploratory in nature. Corresponding 95% CIs will be presented as appropriate. No correction for multiple testing will be applied.

Full details of all statistical aspects and planned statistical analyses will be specified in a separate Statistical Analysis Plan (SAP), which will be finalized prior to the locking of the study database and may include further exploratory analyses not explicitly described in this section, as well as analyses of data from the study phase beyond the main 192week study period, e.g., safety follow-up information.

Analysis populations

The primary effectiveness and safety analyses will be performed using the intent-to-treat (ITT) population. The per-protocol (PP) population will be used for supportive effectiveness analyses of selected effectiveness endpoints in order to evaluate the influence of major protocol violators on key effectiveness endpoints.

ITT Population

All enrolled patients who received any dose of ocrelizumab will be included in the ITT population. Patients who prematurely withdrew from the study for any reason will still be included in the ITT population.

PP Population

The PP population will include all ITT patients without protocol deviations deemed to affect the assessment of effectiveness. The list of criteria leading to exclusion from the PP population will be finalized prior to database closure and documented in the SAP.

Ocrelizumab—F. Hoffmann-La Roche Ltd

85/Protocol MA30143, Version 10.0

Safety Population

The safety population will include all enrolled patients who received any dose or part of a dose of ocrelizumab.

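### The protocol times confirmation of disability improvement (CDI) from a worsening, so taken literally it cannot classify a patient who improves without worsening first

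*Protocol*

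**What the plan says.** Protocol Section 2 (Table 1) and the synopsis list among the effectiveness measures: "Proportion of patients who have confirmed disability improvement (CDI), CDP for at least 24 weeks and 48 weeks at year 1, 2 and 4". Appendix 9, Table 3 uses CDI again, as one of three classes (CDI, CDP, or stable meaning neither) to be correlated with immune markers.

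The only definition of CDI in the supplied documents is in Protocol Section 4.5.6. It opens with "CDI is defined as an improvement of 1 point on the EDSS score" and requires this to be "confirmed at a regular scheduled visit at least 24 weeks after the initial documentation of neurological worsening". A parenthesis limits it: "measured only patients with a baseline EDSS of" 2.0 or more.

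The same section defines progression as an EDSS increase of at least 1.0 point from baseline (with other thresholds for baseline scores of 0 and above 5.5), to be "confirmed at a regularly scheduled visit at least 24 weeks after the initial documentation of neurological worsening".

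The section also defines a separate annual category: "improved disability as a reduction in EDSS score of > 0.5 at the end of each year compared with baseline". That category needs no confirmation and is a different measure.

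Protocol Section 6 leaves full statistical detail to a main-study SAP, to be finalized before database lock. The SAP supplied covers only the shorter infusion substudy, and its Section 4.4 plans no efficacy analysis, so it contains no CDI rule.

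**The concern.** A confirmation rule needs a starting event, and for an improvement endpoint that event should be the first improved score. Here the stated event is a worsening, which is the opposite change. This matters in two ways.

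- Patients who improve directly and hold the improvement, whom the endpoint is meant to count, have no starting date.
- Patients who worsen first do have a starting date, but it says nothing about how long a later improvement lasted.

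The section is the operative definition of a listed endpoint. A programmer who followed it would not obtain a proportion with sustained improvement. In the three-way classification of Appendix 9, a sustained improver who could not be given CDI would fall into the stable class. If the analysis team notices the problem, it will have to choose a working definition itself. It should do so before outcome data are examined: the study is open-label, and Section 6.9 plans exploratory analyses of selected endpoints while it is running.

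**Working it through.** No formula or planned figure is involved. The check compares the two definitions and then applies the CDI rule to short EDSS sequences.

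**The two definitions in Protocol Section 4.5.6**

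| Element | CDP | CDI |
|---|---|---|
| Direction | Increase | Improvement |
| Size | At least 1.0 (other thresholds for some baselines) | 1 point |
| Reference | Baseline EDSS, stated | Not stated; eligibility depends on baseline EDSS |
| Clock starts at | First documented worsening | First documented worsening |
| Confirmation interval | At least 24 weeks | At least 24 weeks |

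The starting event is the same in both columns. It matches the direction of change for CDP and contradicts it for CDI.

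**Search for a correction elsewhere.** The synopsis, Section 2 and Appendix 9 list CDI without defining it. The synopsis and Sections 3.1.3, 3.2 and 6.4.1 mention a CDP/CDI confirmation visit but give no starting event. Section 3.1.3 refers to patients "presenting with an EDSS change at the end of the treatment period", which is neutral on direction. None of these replaces the sentence in Section 4.5.6.

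**Illustrative sequences.** The scores are assumed. The visits follow the EDSS schedule in Appendix 1, which is every 24 weeks from Week 24 to Week 192. Baseline EDSS is 3.0 in both.

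*Patient A: Week 24 = 2.0, Week 48 = 2.0.*
- Change at both visits: 2.0 − 3.0 = −1.0.
- Time between them: 48 − 24 = 24 weeks.
- Literal rule: no worsening is documented, so there is no start date and CDI cannot be assigned.
- Clock started at the first improvement (Week 24): confirmed at Week 48, so CDI.

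*Patient B: Week 24 = 4.0, Week 48 = 2.0, Week 72 = 3.0.*
- Change at Week 24: 4.0 − 3.0 = +1.0, a worsening.
- Change at Week 48: 2.0 − 3.0 = −1.0, seen 48 − 24 = 24 weeks after the worsening.
- Change at Week 72: 3.0 − 3.0 = 0.
- Literal rule: Week 48 can be read as meeting it on a single score.
- Clock started at the first improvement (Week 48): earliest confirmation is 48 + 24 = Week 72, when the improvement has gone, so no CDI.

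The literal rule therefore gives the wrong answer for A and can give the wrong answer for B.

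**Size.** To estimate the effect one would need the share of sustained improvers with no earlier documented worsening. The documents give no such figure. Section 6.1 expects 15% of patients or fewer to have a CDP event by Week 192, but that counts confirmed progression only. It does not bound unconfirmed worsening and does not describe improvers.

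**The case against.** The strongest reply is that this is a copying slip with an obvious meaning. What is being confirmed in the CDI sentence is the improvement, the final clause repeats the CDP sentence, and Appendix 9 treats CDI as a class alongside CDP rather than as something that follows it. An experienced analyst would count from the first improved score, and the main-study SAP may say so. No data are lost, because EDSS is scheduled at the same visits whichever way the score moves. All of this stands and limits the weight of the point. It does not remove it: no supplied document states the intended rule.

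A reader might infer several stronger things that the documents do not support.

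- **That the reported CDI proportion will fall towards zero.** This would follow only if the sentence were programmed literally and nearly all improvers had no earlier worsening. Neither is shown.
- **That improvements of 1.5 points or more would be dropped because the text says 1 point.** Section 3.3 uses 1 point loosely for progression too, beside a definition of 1 point or greater, so an exact-equality reading is strained.
- **That the absent 48-week rule is a fault of CDI in particular.** Section 4.5.6 gives only 24 weeks for CDP as well, while Section 2 names both intervals for both endpoints.
- **That the study's main conclusions are at risk.** Section 6.4.1 says there is no primary endpoint and Section 6.1 says all analyses are descriptive. CDP, EDSS change, relapse, NEDA, NEP, NEPAD and the precision calculations do not use this sentence.

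**Conclusion.** The CDI confirmation rule is wrong as written. Taken literally, it gives no start date for a patient who improves without first worsening, and it could accept one unsustained improved score at least 24 weeks after a worsening. The consequence is limited to the CDI proportions at years 1, 2 and 4 and their use in the immune substudy. Its numerical size cannot be given.

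The conclusion rests on the supplied documents alone. It assumes that the intended starting event is the first documented improvement, which is evident from context but stated nowhere. If the main-study SAP already says this, what remains is a protocol sentence to be brought into line.

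**What to change.** Replace the CDI sentence in Protocol Section 4.5.6 with wording to this effect:

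> CDI is a reduction of at least 1.0 point from baseline EDSS, in patients with baseline EDSS of 2.0 or more, confirmed at a regularly scheduled visit no sooner than 24 weeks (48 weeks for 48-week CDI) after the improvement was first documented.

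Then check that the main-study SAP uses the same rule. The starting event is the correction. The at-least sign, the reference to baseline and the 48-week interval are clarifications to make in the same edit, and the 48-week interval should be added to the CDP definition too.

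The cost is one sentence and a cross-check, with no new visits or data. It is best done before CDI is included in any exploratory analysis and, at the latest, before the main-study SAP is finalized.
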